6.5.3 Other Medications Dosing and Administration**Exenatide (Byetta®) Regimen**

Exenatide will be administered at a dose of 5 mcg subcutaneously given with 1 hour pre-transplant and post transplant bid for 1 week at any time within a 60 minute period before or after the morning and evening meals. After 1 week of therapy, if tolerated well, the dose will be increased to 10 mcg bid. Exenatide will be given for a total of 6 months after the last islet transplant and may be extended if necessary

In addition to prolonged immunosuppression, transplant subjects routinely need other medications (see Section 6.5.4). These include the use of prophylactic anti-infective drugs used in patients receiving prolonged immunosuppression. Anti-infective drugs used under this protocol include trimethoprim / sulfamethoxazole [Bactrim™ single

strength (80 mg TMP/400 mg SMX) 2 tablets po per week] for a minimum period of six months, and valganciclovir (Valcyte®) (450 mg po daily) for 3 months post-transplant. With the use of trimethoprim / sulfamethoxazole and valganciclovir, total WBC counts and kidney function will be monitored at routine visits as shown in Section 6.6.8 *Schedule of Evaluation*. If total WBC counts fall below 3,000, or if other conditions warrant a change in prophylaxis, sulfamethoxazole will be discontinued and substituted with pentamidine 300 mg by inhalation each month for a minimum of six months. Experienced personnel will administer pentamidine with caution, and necessary preparations will be taken to treat acute bronchospasm if it occurs.

During the transplant procedures, additional medications, local anesthetics, and contrast media are also used. Heparin is used during the transplant to reduce coagulation risks that may lead to liver thrombosis. And for 1 week following the transplant, subcutaneous longer acting, low molecular weight heparin (enoxaparin, Lovenox®) is used. Study subjects will be monitored for hemorrhage and bruising while receiving these anticoagulants. Subjects will be expected to self-administer sub-cutaneous doses of Lovenox® 30 mg bid for the week after each transplant or obtain the assistance of another person in doing so.

Other medications may be required according to medical conditions presenting during the study period, and will be given according to best medical practice. For example, filgrastim (Neupogen®) 300 mg sc will be given to post transplant patients presenting with neutropenia secondary to sirolimus, valganciclovir, mycophenolate mofetil, and/or trimethoprim/sulfamethoxazole.

6.5.4 Schedule of Medication

Visit	TX	1	2	3	4	5	6	7	8	9	10	11	12	13	14	15	16	17	18
Week	0	1	2	3	4	6	8	10	12	16	20	24	28	32	36	40	44	48	52
Medication																			
Basiliximab 20 mg iv 2 hours pre-tx and 2 weeks post-tx *	X		X																
Thymoglobulin 1 to 1.5 mg/kg iv for 5 doses **	X																		
Tacrolimus 1 mg po bid. beginning day 1 post-tx	X	X	X	X	X	X	X	X	X	X	X	X	X	X	X	X	X	X	X
Sirolimus 0.2 mg/kg loading dose 2 hours pre-tx , then 0.1 mg/kg po daily	X	X	X	X	X	X	X	X	X	X	X	X	X	X	X	X	X	X	X
Etanercept 50 mg iv 1 hour pre-tx and 25 mg sc on post-tx days 3 7 and 10	X	X	X																
Trimethoprim-sulfamethoxazole 80/400 mg po twice/week	X	X	X	X	X	X	X	X	X	X	X	X							
Valganciclovir (Valcyte®) 450 mg po daily	X	X	X	X	X	X	X	X	X										
Enoxaparin 30 mg sc bid for 7 days	X	X																	
Cefazolin (Kefzol®) 1 gram iv 1 hr pre-tx and q6h for 24 hr after tx	X																		
Exenatide (Byetta®) 5 mcg sc bid for 1 week, then 10 mcg bid.	X	X	X	X	X	X	X	X	X	X	X	X							

Tacrolimus doses will be adapted to reach target trough levels of 3-6 ng/mL; Sirolimus doses will be adapted to reach target trough levels of 10-15 ng/mL during the first 3 months and 7-10 ng/mL thereafter.

**Thymoglobulin will be given only to sensitized patients, the first dose starting before transplantation, followed by 4 subsequent doses on post-transplant days 1, 2, 3, and 4. *Basiliximab will not be given at transplant or 2 weeks post transplant if Thymoglobulin is used.

6.6 Study Evaluations

All subjects will be evaluated and followed at the University of Illinois at Chicago Hospital, Medical Center (outpatient) and Clinical Research Center. Policies and procedures are in place for good clinical practice. Study evaluations and follow-up are detailed in Appendices *Pre-Screening*, *Detailed Visit Schedule*, *Transplant Order*, and *Post-Transplant Orders*, and summarized in Section 6.6.8 *Schedule of Evaluation*.

6.6.1 Pre-Screening

Patients interested in participating in the study will provide Informed Consent to answer a questionnaire regarding their medical history as part of a pre-screening process to select potential candidates and exclude unsuitable subjects from further testing (see Appendix *Pre-Screening*).

6.6.2 Screening

Patients with diabetes who are potentially eligible based on questions asked during pre-screening and continue to express interest will continue with the screening process to determine eligibility. The screening will be organized in two phases (see Appendix *Detailed Visit Schedule*). During phase 1, subjects will provide written Informed Consent to participate in the clinical study and potentially receive investigational islet cell product. Subjects will undergo a detailed history and physical examination and have blood drawn to assess chemistry, hematology, and serologies. A 24-hour urine collection will be obtained, and subjects will have a glucagon stimulation test. Results of these tests will be reviewed, and subjects who remain eligible will undergo further evaluation in phase 2. The evaluations in this phase include additional blood work, cardiac testing, chest x-ray, abdominal ultrasound and Doppler, standard of care primary care screenings, current influenza and pneumococcal vaccines, and ultrasound of the thyroid.

Subjects meeting the inclusion criteria and not presenting with any exclusion criteria will be registered on the UNOS allogeneic pancreatic islet wait list.

The study procedures, risks and potential benefits will be discussed with potential subjects in lay language. The potential subject will have an opportunity to review the subject information and informed consent form and ask questions. Subjects will be assessed for standard islet transplantation at the local site prior to screening, and as a result, will have standard assessment testing per local standard of care, performed prior to signing consent documents. This must be clearly documented and verified within the subject's medical record.

6.6.3 Period on the Waiting List

During phase 3 of the screening period subjects are awaiting their first transplant and will have re-evaluations every 3 months (see Appendix *Detailed Visit Schedule*):

Tests scheduled every 3 months:

- HbA1C

- Comprehensive metabolic panel
- Microalbumin/creatinine ratio
- PRA

Tests scheduled if the subject has not been transplanted within 6 months:

- History and physical
- ECG
- Lab tests to be done in addition to the 3 months schedule
 - CBC
 - PT, PTT, INR
 - HIV
 - Hepatitis panel for hepatitis B and hepatitis C virus
 - VzV IgG if negative at screening phase 2
 - CMV if negative at screening phase 2
 - EBV if negative at screening phase 2
 - RPR
 - Lipid panel
 - Serum pregnancy test

The most recent values for these tests will be recorded in the pre-transplant records.

6.6.4 Immediate Pre-Transplant Work-Up (see Appendix Detailed Visit Schedule and Transplant Order)

Before the transplant the subject will be admitted to the Transplant Unit at the UIC Hospital and the following screening performed to ensure the subject is medically fit to undergo safely the transplant procedure:

- a. History and physical exam
- b. Laboratory studies - STAT
 - Hematology
 - CBC and differential
 - PT-INR, PTT
 - ABO type and cross match
 - Biochemistry
 - Total bilirubin, AST, alkaline phosphatase, albumin, total protein
 - Electrolytes, creatinine, glucose, BUN, magnesium, phosphorous
 - Urinalysis
 - Microbiology
 - Serum CMV IgG & IgM, EBV IgG & IgM
 - C&S and fungi: sputum, urine and blood on subjects who were in hospital during the past week
 - Serum pregnancy test

- Prospective donor-recipient cross match by flow and cytotoxicity sent from the Islet Processing Facility

6.6.5 Transplant Period

During the transplant procedure, the subject will be monitored by continuous ECG, and pulseoxymeter as well as clinically by the transplant surgeon. Capillary blood glucose will be measured every 30 minutes.

Although daily SMPG readings will not be required while in the hospital, the subject should be instructed to continue to complete the diary with all other relevant information (i.e. adverse events).

6.6.6 Early Post-Transplant Period (see Appendix Post-Transplant Orders)

After the islet transplant procedure, subjects will stay for a minimum of 24 hours in hospital with close monitoring in the UIC Hospital Transplant Unit (7W), offering intensive care unit equivalent conditions. Vital signs are monitored every 15 minutes for the first hour, then every 30 minutes for 4 hours, then every 4 hours thereafter until discharge. During the first 24 hours after islet transplantation, liver tests, amylase, lipase, and CBC will be monitored every 8 hours.

Starting at least 4 hours after the islet infusion, subjects will begin a series of treatments with low molecular weight heparin (enoxaparin sodium, Lovenox® 30 mg sc bid, which may be self-administered) for seven days. Hemoglobin will be monitored 3 times during the first week following the transplant procedure.

An ultrasound and Doppler evaluation of the portal system will be performed within 24 hours after each islet transplantation procedure to rule out the possibility of complication including portal thrombus or perihepatic hematoma. If portal vein thrombosis is encountered within a main right or left portal branch within the main portal vein (i.e., main portal vein, but not a segmental peripheral branch), this will be considered a serious adverse event (SAE). In case of portal thrombosis, the subject will receive therapeutic anticoagulation with heparin until reaching a therapeutic INR with oral anticoagulants for a period of 3 months. Ultrasound will be repeated until the portal vein thrombus is resolved.

Subjects will be discharged home 24 hours after transplant if afebrile, having stable hemoglobin, and provided post-transplant Doppler ultrasound is within normal limits. Subjects will be provided with contact information in the event of questions or adverse experiences following discharge.

6.6.7 Post-Transplant Period (see Appendix Detailed Visit Schedule)

Following transplant of islet cells, subjects will monitor their own glucose levels at home. Subjects will be asked to record results in a log for review at the next study visit. Blood samples for analysis (see Appendix *Detailed Visit Schedule*) are drawn three times per

week for the first two weeks and twice a week until the end of the 10th week (see Section 6.6.8 *Schedule of Evaluation*).

Subjects will come to the Clinical Research Center for visits and tests 3 times a week for the first two weeks, then twice per week for another 2 weeks, then weekly until week 12 after transplantation, then gradually tapered to every month during the first year. Additional visits may be necessary. The last study visit will be 52 weeks after transplantation. Additional evaluations may be required for medical conditions presenting during the study period and according to best medical practice.

When a second or third transplant is completed, the follow-up visit schedule is re-started to permit careful follow-up during the immediate post-operative period. In the event a second transplant is not needed due to successful engraftment, insulin independence, and stable blood glucose levels, the follow-up schedule will be maintained at monthly intervals following week 12 through the first year study period according to the *Schedule of Evaluation* in Section 6.6.8.

As in any other transplant situation, medical conditions that arise (e.g., new serious infection, malignancy, compliance issues, etc.) will automatically trigger a re-evaluation to determine if the subject remains qualified for continuous immunosuppression and subsequent transplants, if applicable.

The following laboratories will perform analyses of blood and urine samples:

CMV antibody panel, EBV antibody panel, C-peptide, insulin, anti-islet cell antibodies, anti-IA2, anti-GAD65, and anti-insulin antibodies will be analyzed at:

*ARUP Laboratories
[name]
[name]*

CMVqPCR and EBVqPCR will be analyzed at:

*ViraCor
[name]
[name]*

Inflammatory and detailed lipid panels will be analyzed at:

*CRL Medinet, Inc.
[name]
[name]*

Autologous crossmatch and donor crossmatch will be analyzed at:

*Gift of Hope Organ & Tissue Donor Network Histocompatibility Laboratory
[name]
[name]*

PRA and HLA will be analyzed at:

University of Illinois at Chicago Tissue Typing Laboratory

[name]
[name]

All the other analyses will be performed at:
UIC Pathology Laboratory
[name]
[name].

The following exams and blood test will be performed according to the *Schedule of Evaluation* (see Section 6.6.8 and Appendix *Detailed Visit Schedule*):

- History, and adverse event and toxicity assessments (reviewed at each visit and recorded at any time necessary)
- Physical exam including vital signs (blood pressure, heart rate, respiratory rate, temperature)
- Body mass index (BMI: body weight in kilograms over square of height in centimeters)
- Electrocardiogram (ECG)
- Comprehensive metabolic profile (CMP):
 - Na⁺, K⁺, Cl⁻, Ca⁺⁺, CO₂, creatinine, BUN, glucose, total protein, albumin, total bilirubin, direct bilirubin, ALP, AST, ALT, alkaline phosphatase
- Complete blood count (CBC):
 - Hemoglobin, hematocrit, red blood cells, white blood cells, differential,, platelets
- Serum pregnancy test
- Urine analyses
 - Urinalysis
 - Creatinine, microalbumin, total protein
 - M/c ratio (microalbumin-creatinine ratio) 24-hour specimen at phase 1 screening, and random specimens thereafter unless a 24-hour specimen is medically indicated by elevated results from random sampling
- Drug levels
 - Tacrolimus and sirolimus trough levels to reach target levels defined in Section 6.5.2
- Cytomegalovirus (CMV) viral load by real time PCR
- Epstein-Barr virus (EBV) viral load by real time PCR
- HbA1c, basal C-peptide, fructosamine
- Blood sugar self monitoring (BS-SM)
- Metabolic tests to evaluate insulin-secretory capacity of the islet graft:
 - The following metabolic tests will be done on separate days. The tests are performed after an overnight fast greater than or equal to 10 hours; subjects may drink water. For subjects still on insulin injections, long-acting insulin may be taken no less than 8 hours prior to the test; no food or short-acting insulin may be taken within 5 hours of the test. Humalog should not be taken within 4 hours of the test. If a subject's blood glucose reading is 15 mM or greater (> 270 mg/dL) on the morning of the test, the test will be

rescheduled rather than to perform a procedure which will greatly increase the glucose levels. Additionally, subjects must have consumed at least 150 gm carbohydrate in their diet for the 3 days leading up to the test.

IVGGT, intravenous glucose tolerance test

- An intravenous line is inserted on each arm, and 300 mg/kg of glucose (using a 50% glucose solution) is injected as rapidly as the subject tolerates and within less than 3 minutes. Blood samples for glucose, C-peptide, and insulin measurement are drawn at time -10, -1 (before injection), 2, 3, 4, 5, 6, 8, 10, 15, 20, 30, 40 minutes after glucose injection.
- The acute insulin response will be defined as the mean of the 3, 4 and 5 minutes insulin values with the mean of the basal values (-10 and 0 minute) subtracted.

○ GST, glucagon stimulation test

- Glucose, C-peptide, and insulin levels are measured before and six minutes after injecting a bolus of 1 mg of glucagon (Glucagen[®], Novo Nordisk Pharma SA) or the equivalent intravenously.

○ OGGT, oral glucose tolerance test

- Starting at time 0 the subject consumes a drink containing 75 gm of glucose (in 300 mL solution) over a 5-minute period. Blood samples for glucose, C-peptide, and insulin are drawn before and at 30, 60, 90 and 120 minutes after the subject begins the drink.

○ MMTT, mixed meal tolerance test

- A fasting blood sample for serum glucose, insulin, and C-peptide is drawn just before the test. At time 0, the subject is given Ensure High Protein[®] or Boost[®] to drink in the amount of 6 mL per kg body weight to a maximum of 360 mL, which is to be consumed within 5 minutes. Ninety minutes from time 0, another blood sample is drawn for serum glucose, insulin, and C-peptide.

- Detailed lipid panel
 - Total cholesterol, direct LDL cholesterol, HDL cholesterol, triglycerides, apolipoprotein B, apolipoprotein A1, free fatty acids, and lipid fraction ratio
- Lipid panel
 - Cholesterol, HDL, triglycerides, LDL cholesterol
- Inflammatory panel
 - CRP, MCP, MMP9, CAM, VCAM, fibrinogen, PAI-1 (antigen), TPA
- B-type natriuretic protein (BNP)
- ABO/RH (UNOS requires 2 independent blood type tests)
- Panel reactive antibodies (PRA)
- Antibodies: anti-GAD 65, anti-IA2, anti-islet cell, and anti-insulin
- IL2 receptor saturation
- Archive serum

- Chest x-ray
- Abdominal ultrasound and Doppler
- Thyroid ultrasound (at screening and 52 weeks after final transplant)
- Nuclear renal scan if 24-hour urine corrected creatinine clearance is < 80 mL/min/1.73m² and/or serum creatinine is < 1.2 mg/dL on repeated measurement
- Primary care screening referrals:
 - Women:
 - Mammography annually from age 40
 - Pap test according to current American Cancer Association guidelines
 - Men:
 - Prostate specific antigen (PSA) annually beginning at age 50
 - All subjects
 - Fecal occult blood testing (FOBT) annually
 - Dual x-ray absorptiometry scans (DXA) every 2 years
 - Skin cancer screening annually
 - Dental examination yearly
 - Vision and retina examinations annually
 - Flu vaccine annually
 - Pneumovax according to current CDC guidelines for patients with diabetes or immunocompromising conditions: At least one vaccine and a one-time revaccination if the vaccine was administered > 5 years ago

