**** Alternative immunosuppressant trough level only if applicable**

5-Year Follow-Up

Subjects who complete the original 52-week post-transplant evaluation period will be asked to continue follow-up evaluations every three months for five years for safety and efficacy monitoring. All subjects can voluntarily withdraw from follow-up at any time.

The following examinations and blood tests will be performed according to the *Schedule of 5-Year Follow-Up* (Section 6.7.1). Additional evaluations may be required for medical conditions presenting during the study period and according to best medical practice. Should the function of the islet graft decline over time and the subject return to insulin therapy, repeat transplant may be considered.

- History and adverse event and toxicity assessments (reviewed at each visit and recorded at any time necessary)
- Physical exam including vital signs (blood pressure, heart rate, respiratory rate, temperature)
- Body mass index (BMI, body weight in kilograms over square of height in centimeters)
- Electrocardiogram (ECG)
- Comprehensive metabolic profile (CMP):
 - Na⁺, K⁺, Cl⁻, Ca⁺⁺, CO₂, creatinine, BUN, glucose, total protein, albumin, total bilirubin, ALP, AST, ALT, amylase
- Complete blood count (CBC):
 - Hemoglobin, hematocrit, red blood cells, white blood cells, differential
- Urine analyses
 - Urinalysis
 - Creatinine, osmolality, microalbumin, total protein
 - Microalbumin-creatinine ratio)
- Drug levels
 - Tacrolimus and sirolimus, and alternative trough levels if applicable to reach target levels as defined in Section 6.5.2
- Cytomegalovirus (CMV) viral load by real time PCR
- Epstein-Barr Virus (EBV) viral load by real time PCR
- HbA1c, basal C-peptide, fructosamine
- Blood sugar self-monitoring (BS-SM)
- Metabolic tests to evaluate insulin-secretory capacity of the islet graft:
 - IVGTT – intravenous glucose tolerance test
 - GST - glucagon stimulation test
 - OGTT – oral glucose tolerance test
 - MMTT - mixed meal tolerance test
- Detailed lipid panel:
 - Total cholesterol, direct LDL cholesterol, HDL cholesterol, triglycerides, apolipoprotein B, apolipoprotein A1, free fatty acids, and lipid fraction ratio
- Lipid panel:
 - Cholesterol, HDL, triglycerides, LDL cholesterol
- Inflammatory panel:

- CRP, MCP, MMP9, CAM, VCAM, fibrinogen, PAI-1 (antigen), TPA
- B-type natriuretic protein (BNP)
- Panel reactive antibodies (PRA)
- Antibodies: anti-GAD 65, anti-IA2, anti-islet cell, and anti-insulin

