9.3.5 Exenatide (Byetta®)

Exenatide is an FDA approved incretin mimetic agent that enhances glucose-dependent insulin secretion. Exenatide has also several other antihyperglycemic effects (70). Exenatide will be given to enhance glucose-dependent synthesis of insulin and promote

insulin release from beta cells in the presence of elevated glucose concentrations. Exenatide may also promote islet engraftment through its anti-apoptotic action (53). The known adverse effects of exenatide are mild to moderate hypoglycemia, reduction in appetite, food intake, and/or body weight, headache, and mild to moderate nausea, vomiting, and diarrhea. A gradual titration regimen has been shown to reduce the frequency of nausea. See Appendix *Package Insert Exenatide*

Since October 2007, FDA received reports of six cases of hemorrhagic or necrotizing pancreatitis in patients taking Byetta. All patients required hospitalization, two patients died, and four patients were recovering at time of reporting. Byetta was discontinued in all 6 cases. Byetta and other potentially suspect drugs should be promptly discontinued if pancreatitis is suspected. There are no signs or symptoms that distinguish acute hemorrhagic or necrotizing pancreatitis associated with Byetta from the less severe form of pancreatitis. If pancreatitis is confirmed, the physician must initiate appropriate treatment and carefully monitor the patient until recovery. Byetta should not be restarted. Rodent studies have linked some forms of GLP-1 mimetic therapy with thyroid tumors, but no causal relationship is established in humans (71, 72). Therefore, as a precaution, subjects in this clinical trial will be monitored by periodic thyroid ultrasound scans.

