#### **10.1.1. Definitions**

The following definitions will be applied consistently to the safety analysis:

Baseline (Clinical Labs, Physical Examinations)	The baseline value will be the result collected at the immediate pre-transplant work-up visit, if scheduled, or the most recent screening visit prior to the islet transplant where the lab/examination was scheduled.
Baseline (Vital Signs)	The baseline value will be the result collected at the immediate pre-transplant work-up visit. If this assessment was not obtained, then the most recent value obtained for

	the specific parameter prior to the islet infusion will be used as the baseline value.
Baseline (ECG parameters)	The baseline value will be the most recent pre-transplant value obtained.
Change from baseline	Value at the time point – value at baseline
Treatment-emergent	Any safety assessment that occurred at the onset of or after start of the first islet infusion, up to the end of 1-year follow-up after the last infusion.

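### As printed, year-1 amylase sampling stops 24 hours after each infusion, so the SAP's amylase flag has almost no scheduled data during exenatide treatment; a drafting slip may be the cause

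*Protocol*

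**What the plan says.** **Year-1 panel.** Protocol 6.6.7 lists the CMP as ending "total protein, albumin, total bilirubin, direct bilirubin, ALP, AST, ALT, alkaline phosphatase". ALP and alkaline phosphatase are the same analyte; amylase is absent.

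**Follow-up panels.** The 5-Year Follow-Up section and 6.7 (10-Year Follow-Up) both end the CMP with "total protein, albumin, total bilirubin, ALP, AST, ALT, amylase". These visits are 3-monthly and begin after the 52-week period.

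**Other year-1 amylase.** The grid in Protocol 6.6.8, repeated in SAP 17.1.1, gives amylase its own row with one mark, in the transplant column. Protocol 6.6.6 adds that in the first 24 hours "liver tests, amylase, lipase, and CBC will be monitored every 8 hours".

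**Exenatide.** Protocol 6.5.3: "Exenatide will be given for a total of 6 months after the last islet transplant and may be extended if necessary". Dosing starts an hour before transplant. The 6.5.4 medication table gives "5 mcg sc bid for 1 week, then 10 mcg bid" and marks the drug through week 24. Section 9.3.5 describes pancreatitis reports and says "Byetta and other potentially suspect drugs should be promptly discontinued if pancreatitis is suspected".

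**SAP.** Section 10.3 sets a potentially clinically significant (PCS) criterion for amylase of more than 2 to 5 times the upper limit of normal. It says treatment-emergent PCS values will be identified, and that chemistry values will be summarized at baseline and each follow-up visit. Section 10.1.1 runs the treatment-emergent window from the first infusion "up to the end of 1-year follow-up after the last infusion".

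**The concern.** Followed as printed, the plan measures amylase for about one day around each infusion. It then stops for the rest of the exenatide course and resumes quarterly once the standard course and the treatment-emergent window are over. Amylase is a relevant laboratory marker for the pancreatic risk that the protocol itself raises for exenatide.

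What is at stake is the content behind an SAP commitment. The PCS flag and by-visit summaries would rest on peri-infusion samples plus anything drawn for cause. They would say very little about amylase on exenatide, particularly at 10 mcg twice daily. The trial is meant to support a license application, so on-drug laboratory data for a named risk are worth having when the blood is already being drawn.

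**Working it through.** No sample size or power figure is involved; the check is a count of scheduled draws against the treatment periods.

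**CMP draws per 52-week cycle** (CMP row of Protocol 6.6.8):
- visits 1-2, three draws each: 2 × 3 = 6
- visits 3-7, two each: 5 × 2 = 10
- visits 8-11 (weeks 12-24), one each: 4
- total to week 24: 6 + 10 + 4 = 20
- visits 12-18 (weeks 28-52), one each: 7
- total to week 52: 20 + 7 = 27

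The narrative in 6.6.7 describes somewhat denser blood sampling: three times weekly for two weeks, then twice weekly through week 10. That is 6 + 16 = 22 by week 10, and at least 22 + 4 = 26 by week 24 with the grid draws at weeks 12, 16, 20 and 24. The counts of 20 and 27 are therefore grid counts. On either count, the number that includes amylase is 0 as printed.

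**Amylase values that are scheduled.** 24 h ÷ 8 h = 3 per infusion, plus 1 if the transplant-day mark is a separate sample: 3-4 with one infusion, 9-12 with three.

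**Share of the exenatide course covered.** With one infusion, about 1 day of 168-183, or 0.5-0.6%, all at 5 mcg. With three infusions, assumed 4 weeks apart with 24 weeks of drug after the last, about 3 days of 56 + 168 = 224, or 1.3%. Samples around a second or third infusion could fall on 10 mcg. So the accurate statement is almost none, not none.

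**First follow-up amylase.** Month 3 after the 52-week visit is day 364 + 91 = 455 after the last infusion, about 15 months. That is 455 − 183 = 272 days (about 9 months) after a standard exenatide course ends, and 455 − 365 = 90 days after the treatment-emergent window closes. It would fall on drug only if exenatide were extended that long, or in the window only after a re-infusion.

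**SAP cross-check.** Section 10.3 gives PCS limits for 16 blood tests. Fifteen have scheduled year-1 visit values (CMP 10, blood count 3, lipid panel 1, PRA 1), and the same fifteen have rows in Tables 14.3.10 to 14.3.16. Amylase has neither.

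**Effect of the fix.** With amylase in the year-1 CMP, a single-infusion patient gains 20 scheduled values by week 24 and 27 by week 52.

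**The case against.** The strongest counter-argument is that this is a typing error. The year-1 list has a redundant analyte exactly where the follow-up lists have amylase; if amylase was intended, the sampling gap disappears. The separate transplant-only amylase row counts against a slip, but weakly: the grid also prints direct bilirubin beside the CMP although 6.6.7 already includes it. The Detailed Visit Schedule and Post-Transplant Orders appendices appear only as headings, so further draws cannot be excluded. All of this stands, and it limits the claim to the plan as printed.

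The SAP can also be read as consistent: flagging PCS values applies to whatever values exist, and nothing in the documents ties amylase to exenatide surveillance. Section 6.6.6 groups it with post-procedure liver tests. That is fair, and it makes the change an improvement, not the repair of a broken commitment.

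Four stronger readings are tempting but unsupported:
- *Pancreatitis would be missed.* Section 9.3.5 requires stopping on suspicion, adverse events are reviewed at every visit, and 6.6.7 allows additional evaluations. Clinical cases would be captured.
- *Table 14.3.18 would show a falsely low rate.* It is a by-patient listing with no count or denominator, and each entry shows its assessment.
- *There is no usable baseline.* The work-up in 6.6.4 lists "Total bilirubin, AST, alkaline phosphatase, albumin, total protein" and does not name amylase. But magnesium and phosphorus, marked beside amylase at transplant only, are in that pre-transplant list. A pre-infusion sample is the natural reading.
- *Amylase alone was neglected.* That holds only among blood tests. Urine total protein and urine hemoglobin also have PCS criteria and no summary row, so the PCS list is generally wider than the tables.

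**Conclusion.** The point holds as a modest, inexpensive improvement. On the printed schedule, amylase is on 0 of 20 grid-scheduled CMP draws in weeks 1-24 and 0 of 27 to week 52. Scheduled values cover roughly 1 day of a 168-183 day exenatide course after a single infusion. The SAP 10.3 flag and by-visit summary for amylase therefore have almost no scheduled on-drug data.

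This assumes that the 6.6.7 panel and the 6.6.8 grid are followed literally, that exenatide is not extended past week 52, and that the unavailable appendices add no draws. If the duplicate was meant to be amylase, what remains is wording to correct. No efficacy endpoint and no targeted safety parameter in SAP 2.7.1 depends on amylase.

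**What to change.** In the CMP list of Protocol 6.6.7, replace the duplicate alkaline phosphatase with amylase, to match the follow-up panels, and run it on blood already drawn at least through the exenatide period. Amend the amylase row in Protocol 6.6.8 and SAP 17.1.1 to agree. Check the Detailed Visit Schedule appendix first: if amylase is already there, this is purely a text correction.

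The cost is assay charges and some incidental asymptomatic elevations to review, with no extra visit or draw. The gain is prospective only: it reaches patients still in year 1 (the ongoing group in SAP 5) or re-infused during follow-up under Protocol 6.5.1.

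Three optional clarifications:
- State in 6.6.4 that the transplant-day amylase is taken before infusion, ideally before the first exenatide dose an hour earlier.
- Add an amylase row with the number tested per visit to SAP Table 14.3.15.
- If the omission was intended, footnote Table 14.3.18 to say that, for patients followed before the change, amylase was not routinely assessed between 24 hours after infusion and week 52.

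The last two also help for visits already past.
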